### 2) Objectives\*

This study is intended to study the effects of one-time acute dosing of a solid extract of *Passiflora incarnata*, also known as Passionflower, along with a 10 minute audio-guided mobile meditation on medical students after a didactic examination. Our hypothesis is that blood pressure levels and heart rates, as an assessment of sympathetic tone, will decrease significantly in response to both *Passiflora incarnata* and the meditation.

### 3) Background\*

Elevated blood pressure is a risk factor for development of hypertension later in life, which is a major public health crisis currently, and long-term exposure to high blood pressure may increase the risk of cardiovascular disease (1,6). Hypertension can be caused by an increase in sympathetic tone and/or by an increased heart rate, vasoconstriction, and release of epinephrine and norepinephrine (2). Increased sympathetic output also stimulates the release of renin and, thus, angiotensin II. This ultimately stimulates ACTH release and the release of adrenal glucocorticoids (i.e. cortisol) and aldosterone (3-5).

Meditation is a form of mindfulness that focuses on positive, relaxing thoughts and deep breathing. Medical schools have begun implementing research on the effects of mindfulness on medical students with virtually no evidence of adverse events (7,8). These studies have looked at the effects of meditation and mindfulness over the course of many weeks, whereas our study aims to evaluate its effect for one session only. A 2018 study utilized the mobile application Headspace for 30 days for 10-20 minutes each and found significant improvements in general well-being (9). Literature also supports a positive effect of meditation on blood pressure. One study in pre-hypertensive adults found a significant reduction in systolic blood pressure numbers in those who received 6 months of meditation (10).

*Passiflora incarnata*, commonly known as Passionflower or passionfruit, is a botanical belonging to the *Passifloraceae* family that is traditionally used for anxiety (11). Research has found that it may reduce stress and

UB HRP-503 TEMPLATE: Protocol

PROTOCOL TITLE: Investigating the short-term effects of *Passiflora incarnata* and mobile audio-guided meditation on blood pressure and heart rate in naturopathic medical students

PROTOCOL DATE: 3/28/19

Template Revised: June 14, 2010

anxiety (12-14) with mild and non-serious adverse effects, including headache, abdominal pain, and flatulence. Doses in these trials ranged from 260mg – 700mg. Rare side effects from chronic *Passiflora* use included vasculitis, asthma, rhinitis, and urticaria (15). One case study from 2000 revealed a toxic reaction to *Passiflora incarnata*, in which the patient experienced various cardiovascular effects, including ventricular tachycardia (16). Passionflower extract also contains harmine and hardline which may stimulate uterine contractions, and is therefore contraindicated in pregnancy. It has theoretical action as a platelet inhibitor, so it is contraindicated before surgery. A 2017 trial comparing *Passiflora incarnata* to midazolam before dental extraction found that both *Passiflora* and midazolam improved patients pre-procedure anxiety levels, and they concluded that the *Passiflora* was safe and effective in this one-time dosage (17). 50% of the participants in this trial experienced drowsiness as a side effect of the 260mg preoperative dosage. 20% experienced muscle relaxation, 5% experienced dizziness, 2.5% experienced an allergy, and 2.5% experienced epistaxis. A 2013 study evaluated the effects of 500mg *Passiflora incarnata* on anxiety levels before periodontal treatment. This study found significant reductions in anxiety in those taking the botanical extract with no reports of any adverse effects (18). Lastly, a 2001 study on 36 patients found comparative anxiolytic effects between *Passiflora* and oxazepam with mild-moderate dizziness, drowsiness, impairment of job performance, and confusion listed as the most frequent side effects for both interventions. In the *Passiflora* group, two participants experienced a mild-moderate allergic reaction and two participants experienced mild-moderate ataxia (19). There is no evidence in the current literature that *Passiflora* is an abortifacient or teratogen. To our knowledge, no recent human trials have been done to investigate the effects of *Passiflora incarnata* on blood pressure. A related plant, *Passiflora edulis* has demonstrated antihypertensive properties in rats (20, 21).

#### 4) Setting of the Human Research

The research will take place within the Health Sciences Center on the University of Bridgeport Campus.

We aim to recruit 70 naturopathic medical students for participation in the study in 4 independent groups. Each naturopathic cohort contains between 15-25 students, so we will have 4 different days of research sessions processing 15-25 students each time.

#### 5) Resources available to conduct the Human Research

- The naturopathic medical program currently has 77 students, so we are aiming for a high participation rate from the students.
- Recruitment will take place from May 2019 until August 2019. We expect the research activity to take place during the Fall 2019 semester.
- The UB Naturopathic Clinic has 19 treatment rooms and 1 large classroom which provides ample space for the research to occur.
- We have one pulse-oximetry device for calculating heart rate
- We have five sphygmomanometers for performing manual blood pressure readings
- We need one 4oz. bottle of *Passiflora incarnata* solid extract by Wise Woman Herbals, which has been donated by the company.
- The co-investigators are:

UB HRP-503 TEMPLATE: Protocol

PROTOCOL TITLE: Investigating the short-term effects of *Passiflora incarnata* and mobile audio-guided meditation on blood pressure and heart rate in naturopathic medical students

PROTOCOL DATE: 3/28/19

Template Revised: June 14, 2010

- [name], ND has been associated with the UB Naturopathic Clinic for 3 years as a supervising physician. She has full knowledge of UB Naturopathic Clinic culture and policies.
  - [name], MD who has vast research experience both at UBSNM and at Yale.
  - [name] – Student Research Assistant, current first year ND student, has research and biology experience from Stonybrook University
  - [name] – Student Research Assistant, current second year ND student– has research experience from Eastern Connecticut State University
  - [name] – Student Research Assistant, current second year ND student– has research experience at the University of Bridgeport School of Naturopathic Medicine in the Anatomy Lab with [name]
- In the event of an adverse reaction to the *Passiflora incarnata* extract or the meditation, Student Health Services is available on the first floor of the Health Sciences Building
  - The research team will meet and have a training session before the research session occurs
  - All research team members are CITI-certified

## 6) Study Design

### a) Recruitment Methods

- i) We will recruit from the naturopathic medical program, which currently has 77 enrolled students.
- ii) A flyer will be posted and emailed out to the naturopathic student body (*see Attachment A*)
- iii) Naturopathic student participants will NOT be recruited during class time with [name] or [name] to reduce any conflict of interest or feeling of persuasion that the student may have.
- iv) All naturopathic students will be invited to participate. Once a student expresses interest, he/she will be given the inclusion/exclusion criteria checklist (*see Attachment B*) to ensure eligibility.
  - (1) Exclusion criteria: Those taking hypertensive, blood-thinning, or anti-anxiety medications (including MAOI medications), those with surgery in the past 2 weeks or coming in the next 2 weeks, those females who are currently pregnant or could be pregnant
    - (a) “Day Of” exclusion criteria: consuming food, caffeine, use of stimulant medication, use of MAOI medication, alcoholic beverages, consumption of tyramine containing foods (i.e. blue cheese, gorgonzola cheese, red wine, cured meat, cured fish, sauerkraut, sourdough bread, soy sauce, teriyaki sauce, miso tempeh, or overripe fruits), consumption of cold medicine, antihistamine medication,

UB HRP-503 TEMPLATE: Protocol

PROTOCOL TITLE: Investigating the short-term effects of *Passiflora incarnata* and mobile audio-guided meditation on blood pressure and heart rate in naturopathic medical students

PROTOCOL DATE: 3/28/19

Template Revised: June 14, 2010

decongestant medication, cough suppressant medication, or use of stimulant energy drinks within 2 hours before the study period.

(2) Participants will not be given any incentive to participate (i.e. no payment or “extra credit” will be given).

v) Interested participants will be screened for eligibility (see Attachment B) and allowed to participate if they do not meet any of the exclusion criteria

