**b) Inclusion and Exclusion Criteria\***

i) **Inclusion criteria** – all naturopathic medical students are invited to participate

(1) Participants must have a smartphone with access to the Headspace application and headphones to listen to the session

ii) **Exclusion criteria**

(1) Those taking hypertensive medication

(2) Those taking anti-anxiety medication, including MAOI medication

(3) Those taking blood-thinning medication

(4) Those who are pregnant

(5) Those who could be pregnant

(6) Those who will have surgery 2 weeks before the research date

(7) Those who are scheduled to have surgery 2 weeks after the research date

(8) Those who do not have a smartphone or access to Headspace application

(9) Those who have consumed caffeine, food/tyramine containing foods, stimulant medication, cold medicine, decongestant medicine, antihistamine medicine, cough suppressants, alcoholic beverages, or stimulant energy drinks within 2 hours before the study period.

iii) Interested participants will be contacted by phone or in-person by one of the investigators ([name] or [name]) and screened for exclusion criteria

iv) We aim for 70 subjects to participate but can complete the research with 45-60 subjects to achieve 80-90% power, respectively.

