    - (a) Baseline (15 minutes post-exam) blood pressure readings (three left arm seated readings, average will be calculated) and one heart rate reading taken after at least 5 minutes of rest time without talking, eating, or caffeine consumption.
    - (b) 15 minutes after examination – will be given 1/8 tsp (900mg) of *Passiflora incarnata* solid extract by Wise Woman Herbals mixed with 1/8 tsp of blackstrap molasses to mask the taste and a 10 minute audio-guided mobile meditation session via the Headspace App. Subjects may not consume caffeine or eat food during this time.
    - (c) Three left arm seated blood pressure readings and one heart rate will be taken 15 minutes after the baseline reading.

UB HRP-503 TEMPLATE: Protocol

PROTOCOL TITLE: Investigating the short-term effects of *Passiflora incarnata* and mobile audio-guided meditation on blood pressure and heart rate in naturopathic medical students

PROTOCOL DATE: 3/28/19

Template Revised: June 14, 2010

vii) Safety considerations

- (1) All participants will be given a paper survey about adverse events (*see Attachment C*) which will be returned to the research team by the end of the same study day. Any participant who marks a moderate-severe adverse event will be followed up by [name] for appropriate management.
- (2) [name] phone number and contact information will be given to the study subjects so they can contact her in the event another adverse event arises after the survey has been returned.
- (3) The research will last for about 45 minutes. Three Blood pressure readings (all left arm seated) and one heart rate reading will be taken at baseline and again 15 minutes later.
- (4) Procedures taken to lessen the probability or magnitude of risks
  - (a) Adverse events related to *Passiflora incarnata* use have been found with chronic dosage. We attempt to minimize these risks by providing one-time acute dosage.
  - (b) We are attempting to minimize adverse events by excluding participants who are taking hypertensive medication, anti-anxiety medication, MAOI medication, or blood-thinning medication.
  - (c) We are attempting to minimize adverse events by excluding participants who are pregnant or may be pregnant.

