- (1) Drowsiness (very common, up to 50% reported this adverse effect in studies). Due to this very common side effect, we advise the subject to exercise caution and avoid operating a vehicle or heavy machinery for one hour after taking the dose.
- (2) Muscle relaxation (common, up to 20% reported this in studies). Due to this very common side effect, we advise the subject to exercise caution and avoid operating a vehicle or heavy machinery for one hour after taking the dose.
- (3) Dizziness (common, up to 5% reported this in studies). Due to this very common side effect, we advise the subject to exercise caution and avoid operating a vehicle or heavy machinery for one hour after taking the dose
- (4) Headache
- (5) Abdominal Pain
- (6) Flatulence
- (7) Vasculitis (rare)
- (8) Asthma
- (9) Rhinitis
- (10) Urticaria/Allergic Reaction
- (11) Cardiovascular effects, including Ventricular Tachycardia (one case study, rare)
- (12) Uterine contractions
- (13) Nosebleed, blood-thinning
- (14) Impairment of Job Performance
- (15) Confusion
- (16) Ataxia
- (17) Other unforeseeable adverse reactions

iii) Our exclusion criteria is intended to reduce the risk of adverse events. Our study will involve a one-time acute dosing of *Passiflora incarnata* to reduce the risk of adverse events from chronic, long-term usage.

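### Known passionflower allergy is not a printed exclusion, although allergic reaction is a listed risk of the extract, so the admission rule as written lets such a student in

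*Protocol*

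**What the plan says.** **The risk.** Protocol Section 7(f)(ii)(10) lists "Urticaria/Allergic Reaction" among the possible effects of the extract. Section 3 (Background) reports such events in two cited trials. In the dental-extraction trial, which used a single 260 mg dose, "2.5% experienced an allergy, and 2.5% experienced epistaxis"; its authors nevertheless concluded that the product "was safe and effective in this one-time dosage". In the 36-patient comparison with oxazepam, "two participants experienced a mild-moderate allergic reaction" in the Passiflora group.

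**Who is admitted.** Section 6(a)(iv)(1) summarises the exclusions and Section 6(b)(ii) lists nine. They concern medication (for example "Those taking blood-thinning medication"), pregnancy, surgery, access to the phone and app, and intake within 2 hours of the study period. Section 6(a)(v) then states that screened students are "allowed to participate if they do not meet any of the exclusion criteria".

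**How risk is to be reduced.** Section 6(d)(vii)(4)(a) relates adverse events to chronic dosing and answers: "We attempt to minimize these risks by providing one-time acute dosage". Section 7(f)(iii) says that the exclusion criteria are meant to lower the risk of adverse events and that the single dose is used "to reduce the risk of adverse events from chronic, long-term usage".

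**The concern.** The people most plausibly at risk of an allergic reaction, and the easiest to identify beforehand, are those who already know that they react to passionflower. The protocol recognises the reaction as a risk and says that its exclusions serve to reduce adverse events, yet the printed exclusions pass over this group. Because Section 6(a)(v) turns the absence of a listed exclusion into permission to take part, the omission has a definite result: such a student is eligible and can be allocated to Group III, which swallows 900 mg of the extract.

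What is at stake is participant safety. Eligibility belongs in the protocol and is not something left to a statistical analysis plan.

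**Working it through.** There is no figure to reproduce. The check sets the risk statements beside each rule that might act on them.

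1. **Is the risk recognised?** Yes, in Section 7(f)(ii)(10) and twice in Section 3.

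2. **Does single dosing answer it?** Sections 6(d)(vii)(4)(a) and 7(f)(iii) offer one dose as protection against effects of chronic use. The dental-extraction trial in Section 3 was itself a single-dose trial and reported allergy. Single dosing therefore does not dispose of this risk.

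3. **Does an exclusion cover it?** Section 6(a)(iv)(1) names medications, surgery, pregnancy and same-day intake. Section 6(b)(ii)(1) to (9) names the same and adds lack of a smartphone or the app. Neither names allergy or hypersensitivity. The nearest item is antihistamine use within 2 hours. Section 6(d)(vii)(4)(d) gives the reason for it as interaction with the extract, and an allergic student who has not just taken an antihistamine passes it.

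4. **Does another stated rule cover it?** The remaining mitigation items, Section 6(d)(vii)(4)(b) and (c), deal with medication and pregnancy. The grounds for removing a participant without consent, in Section 6(g)(iii), are device or app failure, not having sat the examination, and prohibited intake.

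5. **Does data collection cover it?** Section 6(d)(vii)(5)(b) collects previous diagnoses and medication in private before the research starts. That may bring an allergy to light, but no stated rule makes it disqualifying.

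6. **What follows?** Under Section 6(a)(v), a student whose only relevant feature is a known passionflower allergy meets no exclusion and is admitted. Section 6(d)(vi)(3)(b) then gives 900 mg if the allocation is Group III.

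7. **How does the protocol treat comparable risks?** Section 3 says that the extract may stimulate uterine contractions, and pregnancy is excluded. It describes platelet inhibition as only theoretical, and surgery within 2 weeks is excluded. Allergy, with cases reported in human trials, has no corresponding exclusion.

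**The case against.** The strongest reply is that this is an omission in the body text, while the working instruments are out of sight. Attachment B is the screening checklist and Attachment D the history questionnaire; either may ask about allergy, and the consent form is not shown. This stands as a limit: the point concerns the printed criteria only. It does not remove the point, because the body states the criteria twice without allergy. If the checklist has the item, the body should match it.

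The second reply is that the harm needs an unlikely sequence. An investigator screens each student, takes a private history and holds a consent conversation of about 20 minutes on a different day. Under Section 6(g)(i) anyone may withdraw at any time. The participants are naturopathic students in a study that openly involves passionflower, and nothing obliges an investigator to dose a student who discloses an allergy. This also stands, and it makes such dosing improbable. These are occasions on which an allergy may surface, however, and not a rule about what then happens. For pregnancy and medication the protocol did not rely on judgement and wrote explicit rules. The adverse event survey and Student Health Services act only after a reaction.

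A reader might infer that no withdrawal route protects the student at all. That goes too far: only the involuntary grounds are silent on allergy, and voluntary withdrawal is open throughout.

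**Conclusion.** The point holds as a limited participant-safety gap in the printed eligibility criteria. It rests on reading Sections 6(a)(iv)(1), 6(b)(ii) and 6(a)(v) as they stand, without Attachments B and D. The number of students affected cannot be estimated from the protocol and may be zero. No endpoint, comparison or power figure is affected.

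Two stronger readings are not supported:

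- **Reading the cited reaction rates as harm that the exclusion would prevent.** With the 2.5% rate and equal allocation (an assumption, since the ratio is not stated), the chance of at least one allergic reaction among n students in Group III is 1 − 0.975^n. That gives 31.6% for n = 15, 39.7% for n = 20 and 44.1% for n = 23, corresponding to totals of 45, 60 and 70. But 2.5% is a rate among treated patients in general. Nothing in Section 3 says that those who reacted knew of an allergy beforehand, so the exclusion might have prevented none of the reactions. The cited cases show that the risk exists, including after one dose, and no more.
- **Inferring a greater allergy risk from the dose.** By stated weight, 900 mg exceeds the 260 to 700 mg range in Section 3, but the relative strengths of the extracts are not given.

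**What to change.** Add *known allergy or hypersensitivity to Passiflora incarnata (passionflower)* to the exclusion criteria in Sections 6(a)(iv) and 6(b)(ii). Put a matching item in Attachment B if it is not already there, and ask it at the existing private screening, before randomisation.

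Naming blackstrap molasses, which Groups II and III both swallow, or related Passiflora species is optional. The protocol reports neither molasses allergy nor cross-reactivity between species.

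The cost is one screening question and possibly a very few students made ineligible. Recruitment should not suffer: if the target of 70 were otherwise met, more than 10 students (70 − 60 = 10; 10/70 = 14.3%) would have to declare an allergy before enrolment fell below 60, the upper of the two sample sizes in Section 6(b)(iv). More than 25 (70 − 45 = 25; 25/70 = 35.7%) would have to do so before it fell below 45, the lower one.

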**b) Inclusion and Exclusion Criteria\***

i) **Inclusion criteria** – all naturopathic medical students are invited to participate

(1) Participants must have a smartphone with access to the Headspace application and headphones to listen to the session

ii) **Exclusion criteria**

(1) Those taking hypertensive medication

(2) Those taking anti-anxiety medication, including MAOI medication

(3) Those taking blood-thinning medication

(4) Those who are pregnant

(5) Those who could be pregnant

(6) Those who will have surgery 2 weeks before the research date

(7) Those who are scheduled to have surgery 2 weeks after the research date

(8) Those who do not have a smartphone or access to Headspace application

(9) Those who have consumed caffeine, food/tyramine containing foods, stimulant medication, cold medicine, decongestant medicine, antihistamine medicine, cough suppressants, alcoholic beverages, or stimulant energy drinks within 2 hours before the study period.

iii) Interested participants will be contacted by phone or in-person by one of the investigators ([name] or [name]) and screened for exclusion criteria

iv) We aim for 70 subjects to participate but can complete the research with 45-60 subjects to achieve 80-90% power, respectively.

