**c) Study Endpoints\***

i) **Primary endpoints:** Blood pressure readings in mm/Hg and heart rate in beats per minute (bpm)

(1) According to the American Heart Association, blood pressure readings are as follows:

(a) Normal: Less than 120/80mmHg

(b) Elevated: 120-129/<80 mmHg

(c) Stage I Hypertension: 130-139/80-89 mmHg

(d) Stage II Hypertension: >140/>90 mmHg

(e) Hypertensive Crisis: >180/>120 mmHg

ii) **Primary safety endpoints:** Adverse events will be recorded for both *Passiflora incarnata* extract and the audio-guided meditation

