**d) Procedures involved in the Human Research\***

i) This will be a randomized, double-blind, placebo controlled trial.

ii) Students will be randomized to Group I, II, or III before the study begins

UB HRP-503 TEMPLATE: Protocol

PROTOCOL TITLE: Investigating the short-term effects of *Passiflora incarnata* and mobile audio-guided meditation on blood pressure and heart rate in naturopathic medical students

PROTOCOL DATE: 3/28/19

Template Revised: June 14, 2010

- iii) Naturopathic medical students will come to the study area in groups of 15-25 (each naturopathic cohort will be studied on a different day)
- iv) Naturopathic medical students will be studied on the day of a classroom examination with three left arm seated blood pressure readings and one heart rate reading taken 15 minutes after the end of the exam and then 15 minutes after that.
- v) All participants will be instructed to download Headspace app onto their smartphone prior to the research date
- vi) The participants will be randomized into three groups
  - (1) Group I
    - (a) Baseline (15 minutes post-exam) blood pressure readings (three left arm seated readings, average will be calculated) and one heart rate reading taken after at least 5 minutes of rest time without talking, eating, or caffeine consumption.
    - (b) This group will not be given any intervention. Subjects will sit quietly for 15 minutes and can read a book, surf the internet, etc. Subjects may not consume caffeine, eat food, or listen to any meditation during this time.
    - (c) Three left arm seated blood pressure readings and one heart rate will be taken 15 minutes after the baseline reading.
  - (2) Group II
    - (a) Baseline (15 minutes post-exam) blood pressure readings (three left arm seated readings, average will be calculated) and one heart rate reading taken after at least 5 minutes of rest time without talking, eating food, or caffeine consumption.
    - (b) 15 minutes after classroom examination – will be given 1/4 tsp of blackstrap molasses placebo and a 10 minute audio-guided mobile meditation session via the Headspace App. Subjects may not consume caffeine or eat food during this time.
    - (c) Three left arm seated blood pressure readings and one heart rate will be taken 15 minutes after the baseline reading.
  - (3) Group III

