  - (d) We are attempting to minimize adverse events by excluding participants who recently consumed cold medicine, cough suppressants, decongestant medication, antihistamine medication, stimulant medication, or tyramine containing foods to avoid interaction with *Passiflora incarnata*.
- (5) Initial data collected from the subjects
  - (a) The inclusion/exclusion criteria data will be collected from the participants before the start of the research (*see Attachment B*). This data will be collected in private with [name] or [name].
  - (b) Age, sex, significant past medical history (previous diagnoses), and medication usage. This information will be gathered via questionnaire (*see Attachment D*) before the start of the research. This data will be collected in private with [name] or [name].
  - (c) Adverse event survey will be collected from the participants by the end of the research day (*see Attachment C*)

e) **Data management\***

- i) Participants will be assigned a de-identifying code upon participation in the research
- ii) This code will be used to randomize the participants into Group I, II, and III
- iii) This code will be placed on both their initial questionnaire, inclusion/exclusion checklist, BP and HR readings, and their adverse events survey

UB HRP-503 TEMPLATE: Protocol

PROTOCOL TITLE: Investigating the short-term effects of *Passiflora incarnata* and mobile audio-guided meditation on blood pressure and heart rate in naturopathic medical students

PROTOCOL DATE: 3/28/19

Template Revised: June 14, 2010

- iv) This code will be linked with the participants' baseline and 15-minute blood pressure readings
  - v) A master sheet linking the code back to the subject's name will be stored on the password-protected University laptop belonging to only the co-investigators in a password-protected Excel sheet.
    - (1) This master sheet will not be printed or emailed between investigators.
  - vi) Hard copies of the inclusion/exclusion criteria checklist, the initial data questionnaire, BP and HR readings, and the adverse event survey will be stored in a locked file cabinet in the primary investigator's office. These forms will be shredded after three years.
  - vii) Power analysis – 45-60 subjects are needed to obtain 80%-90% power, respectively
  - viii) Data analysis will be done by our student research assistants and [name]
- f) Provisions to monitor the data for the safety of subjects\***

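### Does the bare claim that 45-60 subjects give 80-90% power have to be changed?

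*Protocol*

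**What the plan says.** The power claim appears twice in the protocol. Section 6(b)(iv), under the eligibility criteria, reads "We aim for 70 subjects to participate but can complete the research with 45-60 subjects to achieve 80-90% power, respectively". Section 6(e)(vii), under data management, repeats that "45-60 subjects are needed to obtain 80%-90% power, respectively". The two statements agree, and neither lists its inputs.

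The surrounding text leaves several tests open. Section 2 expects that "blood pressure levels and heart rates, as an assessment of sympathetic tone, will decrease significantly in response to both" Passiflora and meditation. Section 6(c)(i) makes blood pressure and heart rate both primary. Section 6(d)(vi) says "The participants will be randomized into three groups": no intervention (I), placebo plus meditation (II), and Passiflora plus meditation (III). The allocation ratio is not stated.

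Section 3 gives no numerical effect on blood pressure or heart rate. On Passiflora it says "To our knowledge, no recent human trials have been done to investigate the effects of" Passiflora incarnata on blood pressure. On meditation it notes that earlier student studies ran for weeks, "whereas our study aims to evaluate its effect for one session only". It cites one blood-pressure trial, of six months of meditation, without giving the size of the reduction.

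Sections 5 and 6(a) give the recruitment frame: 77 enrolled students, all of them invited.

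**The concern.** Power belongs to a stated test against a stated effect. A bare 80-90% attached to a head count cannot be checked, and here several tests are plausible: III against II for Passiflora, II against I for meditation, both together, an overall three-arm test, or a before-after change. The background prints no effect from which a reader could guess the basis.

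The number also does some work. It is the reason given for being able to complete with 45 subjects, which is 25 fewer than the target (25/70 = 36%). If the study ended at 45 and found no difference between III and II, a reader would want to know whether that comparison had had 80% power or much less for the effect the team had in mind. On that view the protocol fixes a minimum sample size on an unverifiable basis, and an analysis plan written later might come too late to repair it.

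**Working it through.** **Inputs from the protocol:** total N of 45 (80%), 60 (90%) and 70 (target), and three arms.

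**Assumptions, since the protocol states neither:** equal allocation, so 45/3 = 15 and 60/3 = 20 per arm; two-sided alpha 0.05. Effects are in SD units of the outcome analysed.

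**Step 1: can the stated figure be reproduced forwards?** No. Without endpoint, contrast, effect and SD there is nothing to put into a formula. The usable check is to invert it: find the effect each point implies, and see whether one effect serves both.

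**Step 2: one between-arm contrast.** By the normal approximation, d = sqrt(2/n) × (1.960 + z_power).
- n = 15, 80%: sqrt(0.1333) × (1.960 + 0.842) = 1.02
- n = 20, 90%: sqrt(0.1000) × (1.960 + 1.282) = 1.03

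By the t test (noncentral t, 2n − 2 degrees of freedom, noncentrality d × sqrt(n/2)):
- n = 15: d = 1.060, noncentrality 2.903, power 80.0%
- n = 20: d = 1.052, noncentrality 3.327, power 90.0%

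The two points imply the same effect to within 0.01 SD.

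**Step 3: overall one-way test of three arms.** The noncentrality is N × f², with f = 0.48.
- N = 45: 45 × 0.2304 = 10.37, on 2 and 42 degrees of freedom, power 80.0%
- N = 60: 60 × 0.2304 = 13.82, on 2 and 57 degrees of freedom, power 91.0%

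In steps of three subjects, f = 0.48 first reaches 80% at exactly 45 and 90% at exactly 60. The published pair is what an ordinary calculation for this design would produce.

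**Step 4: other readings that also fit.** For a before-after change the noncentrality is d × sqrt(n).
- Within one arm: 0.778 SD (n = 15, 80%) and 0.764 SD (n = 20, 90%)
- Pooled over all subjects: 0.427 SD (n = 45, 80%) and 0.425 SD (n = 60, 90%)
- Both adjacent contrasts on one measure (simulated, Group II shared): about 1.22 SD (45) and 1.17 SD (60)

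The implied effect therefore runs from 0.43 to 1.22 SD, a ratio of 2.8. Leaving out the pooled before-after reading it runs from 0.76 to 1.22 SD, a ratio of 1.6.

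**Step 5: what the ambiguity could mean for III against II.**
- Basis 0.43 SD (pooled change): one between-arm difference of that size has about 21% power at 45 and 26% at 60
- Basis 0.77 SD (within-arm change): 53% and 66%
- Basis one between-arm contrast: 80% and 90% for that contrast, but about 61% (d = 1.06) and 80% (d = 1.052) to show both adjacent contrasts on one measure

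**The case for a change.** The strongest case for a change is that this is more than silence left for an analysis plan to fill. The protocol asserts a numerical power and rests a fallback sample size on it. A basis for the sample size normally belongs in the protocol, adding it would take two sentences, and if feasibility really sets the number, a detectable difference would be more candid than an unconditional 80-90%. It stands that the inputs are missing, and that a reader cannot tell whether one part of the section 2 hypothesis is covered or both.

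The rest is weaker. The almost threefold range and the figure of about 20% power come only from the pooled before-after reading. That reading includes the untreated Group I and does not test the randomised comparison; the 21% further assumes that a between-arm difference equals the pooled change over time, which nothing supports. The wording in section 6(b)(iv) is a feasibility statement and contains no rule for stopping recruitment at 45. An analysis plan or power record could perfectly well state the original inputs. Nor does the lack of a printed effect show that none was used: the cited meditation trial may have supplied one, heart rate is also primary, and a conventional standardised effect is possible.

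**Conclusion.** No change follows. The gap is one of reporting: the power figure is stated without its inputs, but it is internally consistent and is not shown to be wrong. Under equal allocation and two-sided alpha 0.05 it matches a single between-arm contrast of about 1.05 SD, or an overall f of about 0.48, both ordinary calculations for three arms.

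Following the protocol as written leaves recruitment, allocation, measurement and analysis exactly as they would be with the inputs written out. With 77 students in the programme, turnout limits the number studied.

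What remains concerns interpretation. An effect of about one SD is large. If one contrast was the basis, the chance of showing both adjacent contrasts on one measure is about 61% at 45 subjects and 80% at 60, so a null result on one of them should be read from its confidence interval and not from the quoted power. All of these figures are back-calculations under the stated assumptions; the sponsor's own basis is unknown.
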